3.4.1.1. Local Reactions

Local reactions (redness, swelling, and pain) at the 13vPnC injection site will be monitored daily for 7 days (Day 1 to Day 7) after each vaccination. An end date will be captured for all reactions either via the e-diary or in the case report form (CRF) as applicable.

Redness and swelling will be measured and recorded in measuring device units for 7 days following vaccination (Day 1 to 7), and then categorized using the scale shown in Table 2 below. The measurements will then be recorded in the e-diary.

A measuring device will be given to the subject’s parent(s)/legal guardian(s)/caregiver(s) with instructions for measuring any redness or swelling at the injection site. Each measuring device unit is equivalent to 0.5 cm. The subject’s parent(s)/legal guardian(s)/caregiver(s) will be asked to measure and to report the largest diameters of a local reaction. In case a measurement is between 2 values, the higher value should be reported. At the time of entry into the e-diary, the subject’s parent(s)/legal guardian(s)/caregiver(s) should record the maximum severity of the reaction since the previous entry into the e-diary.

Pain at the vaccine injection site will be assessed by the subject’s parent(s)/legal guardian(s)/caregiver(s) as mild, moderate, or severe according to the grading scale in Table 2 below.

Table 2. Grading Scale for Local Reactions

| | Mild Grade 1 | Moderate Grade 2 | Severe Grade 3 |
|-------------------------------------|--|---|---|
| Redness | 1 to 4 measuring device units = 0.5 to 2.0 cm | 5 to 14 measuring device units = 2.5 to 7.0 cm | >14 measuring device units = >7 cm |
| Swelling | 1 to 4 measuring device units = 0.5 to 2.0 cm | 5 to 14 measuring device units = 2.5 to 7.0 cm | >14 measuring device units = >7 cm |
| Pain at injection site (tenderness) | Does not interfere with activity | Interferes with activity | Prevents daily activity |

If a local reaction persists beyond the end of the e-diary period, the subject’s parent(s)/legal guardian(s)/caregiver(s) will be requested to report that information and/or any new AEs that develop to the investigator. The investigator will enter this additional information in the subject’s source notes and CRF.

For events that were ongoing on the last day that the e-diary was completed, the end date will be collected in the CRF.

Although the e-diary was designed in such a way that the parent could not skip a question without answering it, the possibility of conflicting responses still exists. For redness and swelling, device units could be recorded with no or missing answer to the root question; or, redness/swelling could be recorded as yes with a measuring device unit of zero (if defaulted by the database). The combination of no with a device unit recorded will result in the answer to the root question being considered yes. The combination of yes with a device equal to 0 will result in the measuring device unit being considered “>0.” A missing value for the root question with a positive value for measuring device units will result in the answer to the root question being considered yes. These rules are summarized in Table 3 below.

Table 3. Data Conventions for Redness and Swelling in the Presence of Inconsistent or Missing Responses

| Present | Reported Response | | Recoded Response | |
|---------|-------------------|------------------------|------------------|------------------------|
| | Present | Measuring Device Units | Present | Measuring Device Units |
| Missing | Missing | Missing | Missing | Missing |
| Missing | 0 | Missing | Missing | Missing |
| Missing | 1-14 | Yes | Yes | 1-14 |
| Missing | 14+ | Yes | Yes | 14+ |
| Yes | Missing | Yes | Yes | Missing |
| Yes | 0 | Yes | Yes | >0 |
| Yes | 1-14 | Yes | Yes | 1-14 |
| Yes | 14+ | Yes | Yes | 14+ |
| No | Missing | No | No | Missing |
| No | 0 | No | No | Missing |
| No | 1-14 | Yes | Yes | 1-14 |
| No | 14+ | Yes | Yes | 14+ |

Redness and swelling will be further categorized according to the following scale based on the recoded responses:

=., if both variables (presence/absence and device units) are missing or otherwise unavailable, or if present and device units are missing;

=0 (absent), if not present and measuring device units are missing;

- =1 (mild), if present and area is 0.5 to 2.0 cm (1 to 4 measuring device units), or if present and measuring device units are “>0”;
- =2 (moderate), if present and area is 2.1 to 7.0 cm (5 to 14 measuring device units);
- =3 (severe), if present and area is >7.0 cm (>14 measuring device units).

In addition, the maximum diameter of the affected area for redness and swelling will be determined. The maximum diameter will be derived as follows:

- =xx (maximum actual value), if present on at least 1 day in the required interval and measuring device units are >0;
- =•, if values are a mixture of absent and missing for required days in the interval;
- =0, if all values are absent for all required days in the interval.

For the purpose of creating an indicator variable for pain at the injection site (tenderness) on each day, the following algorithm will be used:

- =•, if tenderness is missing;
- =0 (absent), if tenderness is not present;
- =1 (mild), if does not interfere with activity;
- =2 (moderate), if some interference with activity;
- =3 (severe), if prevents daily routine activity.

For the local reactions, 3 more derivations are required: whether or not a specific reaction occurred on “any day,” whether or not the subject experienced “any local reaction” on a given day, and whether or not the subject experienced “any local reaction” on “any day.”

For the occurrence of a specific reaction on “any day,” the following algorithm is used and is summarized in [Table 4](#):

- =1 (yes), if the subject reports the specified reaction as yes (or present) on any day in the required interval;
- =0 (no), if the subject reports the specified reaction as no (or absent) for all days in the required interval;
- =•, if the subject reports the specified reaction as a combination of no and missing for all days in the required interval.

Table 4. Derivation of “Each Day” and “Any Day” for Local Reactions in the Presence of Missing Values

| Subject | Day | Response | Each Day | Any Day |
|---------|-----|----------|----------|---------|
| 1 | 1 | Missing | Missing | |
| | 2 | No | No | |
| | 3 | Yes | Yes | |
| | 4 | No | No | Yes |
| 2 | 1 | No | No | |
| | 2 | Yes | Yes | |
| | 3 | Missing | Missing | |
| | 4 | No | No | Yes |
| 3 | 1 | No | No | |
| | 2 | Missing | Missing | |
| | 3 | No | No | |
| | 4 | No | No | Missing |
| 4 | 1 | No | No | |
| | 2 | No | No | |
| | 3 | No | No | |
| | 4 | No | No | No |

For “any local reaction” on a given day, a similar rule applies:

- =1 (yes), if the subject reports any reaction as yes (or present) on the given day in the required interval;
- =0 (no), if the subject reports all reactions as no (or absent) on the given day in the required interval;
- =•, if the subject reports all reactions as a combination of no and missing on the given day in the required interval.

For “any local reaction on any day,” a similar rule applies:

- =1 (yes), if the subject reports any reaction as yes (or present) on any day in the required interval;
- =0 (no), if the subject reports all reactions as no (or absent) for all days in the required interval;
- =•, if the subject reports all reactions as a combination of no and missing.

In summarizing local reactions (over all expected days), the derivation of “any reaction” in the presence of missing values is depicted in [Table 5](#) below.

Table 5. Derivation of “Any Reaction” for Local Reactions in the Presence of Missing Values

| Number of Reactions Reported | Number of Missing Values | Summary Value |
|------------------------------|--------------------------|---------------|
| One or more | None | Reaction |
| One or more | One or more | Reaction |
| None | None | No reaction |
| None | One or more | Missing |

The duration of each reaction will be calculated in days from start of the first reported reaction to resolution of the last reported reaction, inclusive. Resolution information is the last day on which the report was recorded in the e-diary, or the date the reaction ended if it continued beyond Day 7 (or the last record in the e-diary if before Day 7). If there is no known date on which the reaction ended, then duration will be missing. Subjects with no reported reaction have no duration because it is not applicable.

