6.2. Visit 2 - Follow-up Visit (28 to 42 Days After Visit 1)

- Review the subject's e-diary data and collect the e-diary. Collect stop dates of any e-diary events ongoing on the last day that the e-diary was completed and record stop dates in the CRF.
- Determine whether any AEs (including SAEs) have occurred since the last study visit and record them on the CRF (see [Section 8](#)).
- Collect and record any follow-up information on previously documented AEs and SAEs and record their end dates or confirm that they are still continuing.
- Record any nonstudy vaccinations.
- Confirm use of appropriate contraceptives (if appropriate).
- Complete the source documents and the CRFs.

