5.2. General Methods

Unless otherwise explicitly stated, descriptive statistics for continuous variables are n, mean, median, standard deviation, minimum, and maximum. Descriptive statistics for categorical variables are the percentage (%) and the numerator (n) and the denominator (N) used in the percentage calculation.

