5.3. Methods to Manage Missing Data

5.3.1. Safety Data

Handling of missing information related to safety data, such as missing or partially missing date, will be in accordance with Pfizer reporting standards.

For derived variables in reactogenicity data, if any day of the 7-day e-diary is available, the “Day 1 – Day 7” data will be considered as nonmissing for analyses after vaccination. The proportion of subjects with missing reactogenicity data will also be summarized. The denominator will be the number of subjects who receive the scheduled vaccination.

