6.3.2. Reactogenicity Data

The derived endpoints ([Section 3.4.1](#)) for each local reaction and systemic event will be summarized.

The presence and maximum severity of each local reaction and systemic event, including fever, and any event within 7 days following vaccination with 13vPnC, will be summarized by proportions of subjects with the associated 95% Clopper-Pearson CIs.

The presence of each local reaction and systemic event, and any local reaction and systemic event, including fever, on each day and any day of Day 1 to Day 7 following vaccination with 13vPnC, will also be summarized by proportions of subjects with associated Clopper-Pearson CIs.

For each local reaction and systemic event, including fever, descriptive summary statistics of the maximum duration of each event will be provided. The maximum duration of each event for each subject will be calculated as the last day with the event minus the first day with the event + 1, ignoring any intervening days without the indicated event.

For the onset of each local reaction and systemic event, including fever, descriptive summary statistics will be provided.

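### A reaction with no known end date drops out of the duration summary, so the reported maximum can be too low although a minimum duration is known

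*SAP*

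**What the plan says.** SAP 3.4.1.1 counts duration in days from the first reported reaction to resolution of the last, inclusive. Resolution comes from the e-diary, or from the actual end date if the reaction outlasts the diary. The section then adds: "If there is no known date on which the reaction ended, then duration will be missing".

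SAP 5.2 states that "descriptive statistics for continuous variables are n, mean, median, standard deviation, minimum, and maximum". SAP 6.3.2 applies descriptive statistics to each subject's maximum duration, "calculated as the last day with the event minus the first day with the event + 1". It does not say where the last day comes from or what happens when the end is unknown. It does open by saying that the derived endpoints of Section 3.4.1 "for each local reaction and systemic event will be summarized".

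End dates are actively sought. SAP 3.4.1.1: "For events that were ongoing on the last day that the e-diary was completed, the end date will be collected in the CRF". Protocol 6.2, at Visit 2: "Collect stop dates of any e-diary events ongoing on the last day that the e-diary was completed and record stop dates in the CRF". On what is still missing, SAP 5.3.1 says: "Handling of missing information related to safety data, such as missing or partially missing date, will be in accordance with Pfizer reporting standards". Neither document gives a convention for an ongoing reaction, such as a lower bound or a count of reactors left out of the duration summary.

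**The concern.** The exclusion is related to the quantity being summarised. Among reactions followed to the same last contact, those still open are the ones that last longest, and the rule removes exactly these. Something is nevertheless known about each of them: it lasted at least from its first recorded day to the last day it was known to be present. The plan discards that information.

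The only objective of the study is to describe safety, and the maximum is the figure a reader would use to see how long a reaction can last. If the longest reaction is open-ended, the table gives a shorter maximum without a flag.

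The protocol leaves routes to an unknown end date. Protocol 6.2 foresees adverse events still continuing at Visit 2, and Protocol 8.1.4 ends active collection there. Protocol 6.4 allows withdrawal of consent to further data collection.

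**Working it through.** The plan states no duration figure and no expected number of unknown end dates, so there is nothing to reproduce. The check applies the rule to an example.

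**Inputs from the documents**
- The diary covers Day 1 to Day 7, with vaccination on Day 1 (SAP 3.4.1.1, Protocol 6).
- Visit 2 is 28 to 42 days after Visit 1 (Protocol 6.2), so Day 28 + 1 = 29 to Day 42 + 1 = 43.
- Duration = last day − first day + 1 (SAP 6.3.2; SAP 3.4.1.1 counts inclusively as well).
- About 100 subjects are planned (Protocol 3.3).

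**Assumed inputs**
- 19 reactors have known durations: seven of 1 day, six of 2, four of 3 and two of 4. The sum is 7×1 + 6×2 + 4×3 + 2×4 = 39.
- One further reactor has no known end date.

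**Results**
1. SAP 3.4.1.1 as written: the open case is missing. n = 19, mean 39/19 = 2.05, median 2, maximum 4.
2. Open case with onset Day 2, present on Day 7: minimum duration 7 − 2 + 1 = 6. The maximum is known to be at least 6, and the table reports 4. Counted at 6, the mean is (39 + 6)/20 = 2.25.
3. Same onset, confirmed ongoing at Visit 2: minimum duration 29 − 2 + 1 = 28 to 43 − 2 + 1 = 42. The table still reports 4. Counted at the minimum, the mean is (39 + 28)/20 = 3.35 to (39 + 42)/20 = 4.05.
4. Open case from a diary that stopped after Day 1: minimum duration 1 − 1 + 1 = 1. The known maximum stays at 4. Counted at 1, the mean is (39 + 1)/20 = 2.00, slightly below 2.05.

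The median is 2 in all four. The maximum is understated on known facts only when the open case's minimum exceeds every known duration. The means in 2 to 4 use lower bounds and do not estimate the true mean; they show only that the shift has no fixed sign.

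**Chance of at least one such case.** With an assumed rate q per subject and 100 subjects, the chance is 1 − (1 − q)^100: 9.5% at q = 0.1%, 39.4% at 0.5%, 63.4% at 1% and 86.7% at 2%.

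**The two duration statements side by side.** For onset Day 2 and a CRF end date of Day 20, SAP 3.4.1.1 gives 20 − 2 + 1 = 19, and SAP 6.3.2 gives the same 19 if its last day is the CRF date. Only a reading confined to diary days gives 7 − 2 + 1 = 6. With no end date, SAP 3.4.1.1 gives missing and the diary-day reading gives 6.

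**The case against.** The strongest objection is that little is lost. Duration is a descriptive display in a study without hypotheses. Persisting reactions are reported to the investigator (Protocol 7.3.1, 7.3.2), Day 7 fever is followed to resolution (Protocol 7.3.3), and subjects who miss a visit are pursued (Protocol 6.4). Protocol 9.2 lists events that persist beyond Day 7. The number left out can be found by subtracting the n for duration from the number with the reaction. This stands as a limit on size: cases should be few and partly visible. It does not correct the maximum in the table, and the listing does not clearly cover a diary that stopped before Day 7 with a reaction ongoing. Nor does SAP 5.3.1 fill the gap. Its sponsor standards are not shown, and it treats Day 1 to Day 7 data as nonmissing "if any day of the 7-day e-diary is available", so its missing-data summary would not count a recorded reaction that lacks only an end date.

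A second objection is that SAP 3.4.1.1 can be read as taking the last diary record as the resolution date when a diary stops early. Result 4 would then not arise. That reading is less natural, because the same section sends events ongoing at the last completed diary day to the CRF for their end date.

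A reader might infer that SAP 6.3.2 contradicts SAP 3.4.1.1. The documents do not support that. SAP 6.3.2 points to the Section 3.4.1 endpoints, and on CRF dates the two agree. What remains is a clarification: SAP 3.4.1.2.1 carries duration over to fever, but SAP 3.4.1.2.2 does not name duration among the further derivations for the other systemic events.

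**Conclusion.** The point holds, with limited consequence. The rule is explicit, it can remove the longest reaction, and the reported maximum can then lie below a duration already known. In the example the table reports 4 days where at least 6 are known, or at least 28 to 42 if the reaction is ongoing at Visit 2. These sizes rest on assumed durations and a single assumed open case; with no open case there is no effect.

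A reader might go further and infer that mean duration is biased downward or that the primary safety results are compromised. Neither follows. The direction for the mean is undetermined, and the occurrence and severity proportions with their confidence intervals do not use the end date.

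**What to change.** For each local reaction and systemic event, including fever, SAP 6.3.2 should:
- show the number of reactors with no known end date;
- give their minimum duration as '≥ (last day known present − first day present + 1) days', so that onset Day 2 and presence on Day 7 prints as ≥ 6, not ≥ 7;
- show the maximum as '≥ x days' when such a reaction is the longest;
- keep the mean and SD on reactions with known end dates, with a footnote saying so.

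As a clarification only, SAP 6.3.2 should state that the last day is the diary or CRF end date as defined in SAP 3.4.1.1, and that this also applies to the non-fever systemic events.

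The cost is SAP wording and minor programming on data already collected, and a slightly less tidy table.

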3.4.1.2. Systemic Events, Including Fever

The systemic events reported in the e-diary following vaccination are fatigue, headache, vomiting, diarrhea, muscle pain, and joint pain. These will be recorded as present or absent. Fever is also included as a systemic event.

3.4.1.2.1. Fever

The subject’s temperature will be recorded in the e-diary for 7 days following vaccination (Day 1 through Day 7, where Day 1 is the day of vaccination). If more than 1 temperature was taken for a subject on the same day, the highest temperature will be recorded in the e-diary.

The protocol defines fever as a temperature $\geq 100.4^{\circ}\text{F}$ (or $\geq 38.0^{\circ}\text{C}$). In the event of a fever on Day 7, temperature will be measured daily until fever has resolved (1 day of temperature less than 100.4°F [38.0°C]) in order to collect a stop date in the CRF.

Temperature will be measured and recorded to 1 decimal place and then grouped into ranges for the analysis according to Table 6 below.

Table 6. Ranges for Fever (All Subjects)

| | | | | |
|-------|--------------------|--------------------|--------------------|----------|
| Fever | 38.0°C to 38.4°C | 38.5°C to 38.9°C | 39.0°C to 40.0°C | >40.0°C |
| | 100.4°F to 101.1°F | 101.2°F to 102.0°F | 102.1°F to 104.0°F | >104.0°F |

Fever will be classified for a given day based on the following scale:

- =●, if temperature is missing, or otherwise unavailable
- =0 (absent), if temperature is not missing and <38.0°C (100.4°F)
- =1, if temperature is ≥38.0°C (100.4°F) but ≤38.4°C (101.1°F)
- =2, if temperature is ≥38.5°C (101.2°F) but ≤38.9°C (102.0°F)
- =3, if temperature is ≥39.0°C (102.1°F) but ≤40°C (104.0°F)
- =4, if temperature is >40.0°C (104.0°F)

Similar to the derivations specified for local reactions, any day, any fever, any fever on any day, and duration of fever will be derived. Duration will be calculated for any fever (temperature ≥38.0°C [≥100.4°F]). Each category of fever will be included as a separate event in summaries of systemic events.

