7.3.3. Fever

A digital thermometer will be provided with instructions on how to measure the subject's temperature at home. Temperature will be collected in the evening daily for 7 days following vaccination (Day 1 through Day 7, where Day 1 is the day of vaccination) and at any time during the 7 days after Visit 1 that fever is suspected. Fever is defined as a temperature of $\geq 100.4^{\circ}\text{F}$ ($\geq 38.0^{\circ}\text{C}$). The highest temperature for each day will be recorded in the e-diary.

In the event of a fever on Day 7, temperature will be measured daily until fever has resolved (1 day of temperature less than 100.4°F [38.0°C]) in order to collect a stop date in the CRF.

Temperature will be measured and recorded to 1 decimal place and then grouped into ranges for the analysis according to Table 3 below:

Table 3. Ranges for Fever (All Subjects)

Fever	38.0°C to 38.4°C	38.5°C to 38.9°C	39.0°C to 40.0°C	>40.0°C
	100.4°F to 101.1°F	101.2°F to 102.0°F	102.1°F to 104.0°F	>104.0°F

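### Two Fahrenheit fever limits (101.2°F and 102.1°F) do not equal the Celsius limits they are paired with, and no recording unit or conversion rule settles which applies

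*SAP*

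**What the plan says.** SAP section 3.4.1.2.1 defines the daily fever variable by four ranges, each with its limits in °C and a °F figure in parentheses:

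- Range 1: "if temperature is ≥38.0°C (100.4°F) but ≤38.4°C (101.1°F"
- Range 2: "if temperature is ≥38.5°C (101.2°F) but ≤38.9°C (102.0°F"
- Range 3: "if temperature is ≥39.0°C (102.1°F) but ≤40°C (104.0°F"
- Range 4: "if temperature is >40.0°C (104.0°F"

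SAP Table 6 prints the same pairs. So does protocol Table 3 (section 7.3.3), where the range from 38.5 to 38.9°C is paired with "101.2°F to 102.0°F".

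On precision the SAP says: "Temperature will be measured and recorded to 1 decimal place and then grouped into ranges for the analysis according to Table 6 below". Neither document says whether the e-diary holds °C or °F, or how one is turned into the other.

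On reporting it says: "Each category of fever will be included as a separate event in summaries of systemic events". SAP section 6.3.2 then asks for proportions with Clopper-Pearson 95% intervals for the presence and maximum severity of each systemic event, fever included. Systemic events within 7 days are a primary endpoint (SAP section 3.1).

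**The concern.** The scale treats the two units as interchangeable, so a given temperature should land in the same range whichever unit is used. If a paired limit is not a true conversion, two programmers could each follow the SAP and count the same child in different ranges. Because every range is tabulated as its own event for a primary endpoint, the discrepancy would reach reported proportions and intervals.

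Fahrenheit recording cannot be ruled out. The fever definition in protocol section 7.3.3, its restatement in the SAP and the vaccination-delay criterion in protocol section 4.3 all put °F first. The thermometer is described only as digital.

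**Working it through.** **Inputs.** The paired limits come from SAP section 3.4.1.2.1 and Table 6, and are identical in protocol Table 3. Readings are recorded to 1 decimal place.

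**Step 1: convert each °C limit.** F = 1.8 × C + 32.

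| °C limit | Calculation | Exact °F | Printed °F | Agrees at 1 decimal |
|---|---|---|---|---|
| 38.0 | 68.40 + 32 | 100.40 | 100.4 | yes |
| 38.4 | 69.12 + 32 | 101.12 | 101.1 | yes |
| 38.5 | 69.30 + 32 | 101.30 | 101.2 | **no** |
| 38.9 | 70.02 + 32 | 102.02 | 102.0 | yes |
| 39.0 | 70.20 + 32 | 102.20 | 102.1 | **no** |
| 40.0 | 72.00 + 32 | 104.00 | 104.0 | yes |

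Four of the six limits reproduce. The other two are exact at 1 decimal, so rounding does not explain the printed values. The pattern suggests that each upper limit was converted and the next range was then started 0.1°F above it.

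**Step 2: convert the readings at the two boundaries back.** C = (F − 32) / 1.8.

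| Reading (°F) | Calculation | Exact °C | Range by °F limits | Range by °C limits, rounded to 1 decimal | Range by °C limits, unrounded |
|---|---|---|---|---|---|
| 101.1 | 69.1 / 1.8 | 38.389 | 1 | 1 (38.4) | 1 |
| 101.2 | 69.2 / 1.8 | 38.444 | 2 | 1 (38.4) | none |
| 101.3 | 69.3 / 1.8 | 38.500 | 2 | 2 (38.5) | 2 |
| 102.0 | 70.0 / 1.8 | 38.889 | 2 | 2 (38.9) | 2 |
| 102.1 | 70.1 / 1.8 | 38.944 | 3 | 2 (38.9) | none |
| 102.2 | 70.2 / 1.8 | 39.000 | 3 | 3 (39.0) | 3 |

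The two unrounded values fall between the °C ranges, in the gaps from 38.4 to 38.5 and from 38.9 to 39.0.

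**Step 3: look for other disagreements.** Every 0.1°F reading from 99.0 to 105.9 was classified under both sets of limits. Only 101.2 and 102.1 disagree. In the other direction, every 0.1°C reading from 37.5 to 41.1, converted to °F and rounded to 1 decimal, stays in its own range.

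**Step 4: check what is untouched.** The fever threshold is exact (38.0°C = 100.4°F), and so is the start of range 4 (40.0°C = 104.0°F). The SAP calculates duration for any fever, not by range. Presence, the any-fever proportion, duration and range 4 therefore do not depend on the unit.

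**Step 5: size per child.** With about 100 subjects (protocol section 3.3), one child moved changes a range's proportion by 1/100 = 1 percentage point. For an otherwise empty range, 0/100 has an exact 95% interval of 0 to 3.6% (upper limit 1 − 0.025^(1/100)); 1/100 has 0.03% to 5.4%.

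**The case against.** The strongest reply is that the scale is usable as printed. At 0.1°F steps the °F ranges have no gap and no overlap, so a team working wholly in °F would classify every reading once. A team working wholly in °C would also classify every recorded value once. On that view the fault is an inexact label and a missing conversion rule.

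Much of this stands. A reader might infer that the rule contradicts itself outright, or that the two readings are plainly put one range too high. The documents do not support either inference without a further assumption. One range too high is true only if the converted value is rounded to 1 decimal, and neither document says to do that. Taken literally, 38.44°C and 38.94°C meet no °C range at all. This caveat applies equally to both readings.

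A reader might also take the two affected readings, out of the 37 possible 0.1°F values from 100.4 to 104.0°F, as a measure of impact. That is a count of points on a scale, not of children. The documents give no fever rate, and the effect is nil if recording is in °C. The study is also descriptive, with no hypothesis test or decision rule (SAP section 5.1), so no conclusion turns on a range boundary.

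What the reply does not remove is that two printed equivalents are wrong in both documents, that nothing else corrects them, and that the unit is left open.

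**Conclusion.** Wrong as written, with a small effect. The °F lower limits of ranges 2 and 3 are each 0.1°F below the °C limits they are paired with. That is arithmetic and rests on no assumption.

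The consequence is conditional. It needs temperatures recorded in °F, and a child with a daily reading of exactly 101.2 or 102.1. In that case the range depends on which column is used and on whether the converted value is rounded. Only the counts in ranges 1, 2 and 3 can shift, by about 1 percentage point per child affected. How many children that might be cannot be estimated from the documents. A reading that the fever rate itself is in doubt would be mistaken, because the 38.0°C threshold converts exactly.

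**What to change.** 1. Add a sentence to SAP section 3.4.1.2.1: °F readings are converted to °C, rounded to 1 decimal place and classified by the °C limits. This alone settles the analysis. Relabelling alone would not, since unrounded values could still fall between the °C ranges. Fixing a single recording unit would also work, if the e-diary allows it.
2. Correct the °F labels to 100.4–101.2, 101.3–102.1, 102.2–104.0 and >104.0°F. With these, every 0.1°F reading falls in the same range as its °C value rounded to 1 decimal. The new upper labels are the highest 0.1°F readings that round to 38.4 and 38.9°C, not direct conversions of those limits; a footnote should say so.
3. Align protocol Table 3 at the next amendment.

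**Cost.** Four printed figures change in SAP Table 6 and the same four in the scale: 101.1 to 101.2, 101.2 to 101.3, 102.0 to 102.1, and 102.1 to 102.2. Protocol Table 3 needs the same four changes. A protocol amendment needs prospective ethics approval (protocol section 12.1), so one for this alone is hard to justify. Protocol section 9 and SAP section 2 let the SAP modify the analysis plan short of a major change to a primary endpoint, and in my judgement this is not major. No new data are needed, and the fever definition is unchanged.
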